5.1.2 Treatment Period

At the Day 1 study visit, participants who have met the eligibility criteria for this study will be assigned a unique study identification number ([Section 7.2](#) [Method of Treatment Assignment]) and study treatment will be dispensed. On Day 1, after the informed consent is obtained, study treatment should be taken at the site from Study IM011077.

Prior to each scheduled visit, the participant [REDACTED] should be reviewed to ensure [REDACTED] stool frequency (SF) and RB data [REDACTED] for participants with UC. Prior to each scheduled visit at which Mayo scores are to be calculated, study personnel should ascertain whether an adequate number of days [REDACTED] have been made. If adequate [REDACTED] have not been made, the site should contact the participant to reschedule the visit (within the allowed [REDACTED]) to allow time for a sufficient number [REDACTED] for endpoint assessments, and the participant should be counseled about proper study procedures.

[REDACTED] It is recommended that the endoscopy be done as close as possible to the relevant visit.

If a colonoscopy is performed at the end of treatment visit of the parent study, colonoscopy will be the preferred endoscopic procedure for subsequent endoscopies within the study. This approach will facilitate comparison between the individual colonic segments assessed at the Day 1 visit and subsequent assessments.

Discontinuation criteria are detailed in [Section 8](#). Participants who temporarily discontinue study treatment will remain in the study and continue to participate in study procedures ([Section 8.1.1](#)).

Participants who permanently discontinue study treatment will complete an early termination (ET) visit and must enter the 4-week post-treatment follow-up period and complete the final safety visit.

5.1.3 Follow-up Period

Participants who complete the treatment period (ie, Week 288) or permanently discontinue study treatment at any time during the study (Section 8) will enter a 4-week post-treatment follow-up period and complete the final safety visit.

5.1.4 Treatment Failure

For the purpose of this study, treatment failure will be defined as:

- 1) Requirement for [REDACTED] over the course of a participant's time on study due to increased CD or UC activity, [REDACTED]
[REDACTED]
[REDACTED]
[REDACTED]
[REDACTED]
[REDACTED]
- 2) Requirement for an alternative, efficacious therapy for CD or UC (eg, initiation of biologics, prednisone (or equivalent) [REDACTED] daily).
OR
- 3) Participants with CD with a loss of response at [REDACTED] with loss of response defined as:
[REDACTED]
[REDACTED]
OR
- 4) Participants with UC with disease worsening at [REDACTED] apart, with a worsening of clinical disease activity defined as:

5) Participants requiring a [REDACTED] symptoms.

5.1.5 Data Monitoring Committee and Other External Committees

An external, independent DMC will provide oversight on the safety of trial participants within this study. The DMC will regularly review accumulating data from this study and advise the Sponsor regarding the continuing safety of trial participants, as well as the continuing validity and scientific merit of the trial.

Data summaries and listings will be provided to the DMC to facilitate their safety assessment at regularly scheduled meetings and on an ad hoc basis if needed. The DMC will also be provided with suspected, unexpected serious adverse reaction (SUSAR) reports relating to deucravacitinib and recommendations from other DMCs supporting the deucravacitinib clinical development program.

Regular DMC safety reviews will include all AEs, SAEs, and AEIs. Based on their review of safety data, the DMC will make recommendations regarding the appropriateness of continuing the study, with or without study modifications, or stopping the study. The DMC may request select efficacy data from the blinded parent studies for benefit-risk assessment and study continuation.

Additional details on the DMC's processes and procedures will be outlined in the DMC Charter.

5.2 Number of Participants

Approximately 300 participants are expected to rollover from the parent studies into Study IM011077. All participants must have completed 1 of the parent studies (Studies IM011023, IM011024, or IM011127) and must meet all eligibility criteria as specified in [Section 6.1](#) (Inclusion Criteria) and [Section 6.2](#) (Exclusion Criteria).

5.3 End-of-Study Definition

The start of the trial is defined as the first visit for the first participant enrolled. End of trial is defined as the last scheduled procedure shown in [Section 2](#) (Schedule of Activities). Study completion is defined as the final date on which data were or are expected to be collected. [REDACTED]

5.4 Scientific Rationale for Study Design

This is an open-label, multicenter study to evaluate the long-term safety and efficacy of deucravacitinib 6 mg BID in participants with moderate to severe UC and moderate to severe CD.

Deucravacitinib acts by inhibiting TYK2, a protein involved in IL-12 and IL-23 signaling, in addition to Type I IFN signaling. Deucravacitinib allosterically inhibits the kinase activity of TYK2 by binding to the regulatory pseudokinase JH2 domain, which prevents receptor-stimulated activation of TYK2.^{12,27} The TYK2 locus is associated with IBD in genome-wide association studies.²⁸ Carriage of a naturally occurring variant in TYK2 is associated with a reduced risk of IBD.^{23,29} [REDACTED]

[REDACTED]

The IL-12/IL-23 axis has been implicated in the pathogenesis of IBD in humans,¹⁴ as described in [Section 3.2](#) (Background). These data from antibodies under development^{13,19,20} and the commercial availability of ustekinumab^{16,17,30} provide proof of concept that IL-23 inhibition (either alone or together with IL-12 inhibition) is likely to be therapeutically beneficial in patients with active CD or UC. Providing an opportunity for participants who are likely to derive benefit from long-term dosing with deucravacitinib to continue into this study will allow further evaluation of the long-term safety and efficacy in this patient population.

As a long-term safety and efficacy study, the intent is to assess both the safety and tolerability of long-term exposure to deucravacitinib and the maintenance of clinical response and other efficacy endpoints seen in the parent studies. This study will estimate the effect of deucravacitinib on efficacy using standard CD and UC efficacy instruments to determine eligibility and assess efficacy ([Section 9.1](#)).^{31,32,33} Disease activity eligibility criteria are clearly defined in [Sections 6.1](#) and [6.2](#).

[REDACTED] This approach is intended to maximize the efficacy data acquired in this study. Design elements in the current study, namely inclusion/exclusion criteria and safety and efficacy assessments, are based on the design of the phase 2 parent studies. This is designed to facilitate both separate and integrated analyses of exposure/clinical response and exposure [REDACTED] response, which may inform the selection of a deucravacitinib regimen to be evaluated in an adequately powered Phase 3 clinical trial program.

[Section 3.3](#) contains an additional discussion on the benefit-risk profile of this study.

Justification of the dose levels used in this study is discussed in [Section 5.5](#).

The rationale for the study's sample size is discussed in [Section 10.1](#).

5.5 Justification for Dose

The recommended 6-mg BID dose is based on the current understanding of the PK/PD relationship for deucravacitinib. [REDACTED]

[REDACTED] Additional assessments based on competitor IL-12 and IL-23 antibodies also support higher and more frequent dosing to provide robust efficacy. The recommended dose is based on implementation of appropriate safety margins and is within the range of doses tested in the first-in-human study, Phase 2 psoriasis and other indications, and is also within margins based on comparisons of systemic exposure and body surface area.

The following points were considered for dose selection:

- 1) The data from preclinical studies of deucravacitinib that showed an exposure-response relationship between deucravacitinib PK, target engagement assays, and efficacy indicators of interest in animal models of IBD.
- 2) CD, UC, and psoriasis are all highly dependent upon the IL-17/IL-23 pathway.³⁵ Thus, the observed efficacy and dose response observed in psoriasis are assumed to be informative for dose selection in CD and UC.

█ Additionally, other IL-12/IL-23 inhibitor antibodies (ustekinumab and risankizumab) have also demonstrated that higher dose and more frequent dosing is required for IBD relative to the dosing in psoriasis. The preclinical data and competitive data support a higher dose (6 mg/day) and more frequent dosing (BID dosing) of deucravacitinib in IBD patients.

- 3) The PK properties and target engagement assessment in healthy volunteers were also used to inform the dose selection. █
- 4) All participants entering this study (Study IM011077) from the parent studies will have received deucravacitinib at 6 mg BID for a minimum of █ weeks (Study IM011127) up to █ weeks (Studies IM011023 and IM011024) prior to entering. With eligibility dependent on participants' demonstration of clinical response at the end of the parent study with an acceptable safety profile, continuing participants at this dose for the long-term extension would be appropriate.

6 STUDY POPULATION

For entry into the study, the following criteria MUST be met.

6.1 Inclusion Criteria

1) Signed Written Informed Consent

- a) Participants must be willing to participate in Study IM011077 and must have the ability to sign the informed consent form.
- b) Willing and able to complete all study specific procedures and visits.

2) Type of Participant and Target Disease Characteristics

- a) Previously completed OLE treatment in 1 of the parent CD or UC studies;
- b) Be in clinical response or clinical remission at Week 104 of Study IM011023 or Study IM011024, or Week 52 of Study IM011127;

- i) Evidence of clinical response or clinical remission (compared with baseline in the parent study) as defined by CDAI (refer to [Table 4-3](#) [REDACTED]) or modified Mayo score (refer to [Table 4-3](#) and [Appendix 13](#));
AND
- ii) No worsening of endoscopy (by SES-CD [refer to [REDACTED] or Mayo endoscopic subscore [refer to [Appendix 13](#)]) from the parent study baseline (as assessed by local read).

3) Age and Reproductive Status

Investigators shall counsel women of childbearing potential (WOCBP) participants, and male participants who are sexually active with WOCBP, on the importance of pregnancy prevention and the implications of an unexpected pregnancy.

- The investigator shall evaluate the effectiveness of the contraceptive method in relationship to the first dose of study intervention.
- Local laws and regulations may require the use of alternative and/or additional contraception methods.

a) Female Participants

- i) Females, age 18 or local age of majority and older at the time of enrollment.
- ii) Women who are not of childbearing potential are exempt from contraceptive requirements.
- iii) Women participants must have documented proof that they are not of childbearing potential.
- iv) WOCBP must have a negative highly sensitive urine pregnancy test (minimum sensitivity 25 IU/L or equivalent units of human chorionic gonadotropin) within 24 hours prior to the start of study treatment.

If a urine test cannot be confirmed as negative (eg, an ambiguous result), a serum pregnancy test is required. In such cases, the participant must be excluded from participation if the serum pregnancy result is positive.

- v) For additional requirements for pregnancy testing during and after study intervention, see [Section 2](#) (Schedule of Activities).
- vi) The investigator is responsible for review of medical history, menstrual history, and recent sexual activity to decrease the risk for inclusion of a woman with an early undetected pregnancy.
- vii) WOCBP must agree to follow instructions for method(s) of contraception defined in [Appendix 4](#) and as described below and included in the ICF.
- viii) WOCBP are permitted to use hormonal contraception methods as described in [Appendix 4](#).
- ix) A female participant is eligible to participate if she is not pregnant or breastfeeding and at least one of the following conditions applies:
 - (1) Is not a WOCBP,

OR

- (2) Is a WOCBP and using a contraceptive method(s) as described in [Appendix 4](#), during the treatment period (at a minimum until after the last dose of study treatment).
- b) Male Participants
- i) Males, age 18 or local age of majority and older at the time of enrollment.
 - ii) Male participants should maintain their usual practice with regard to contraception (if any); however, no specific contraceptive measures are required.

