2 SCHEDULE OF ACTIVITIES

Table 2-1: Day 1 Procedural Outline IM011077 From Parent Study IM011023 - Crohn’s Disease

Procedure	Day 1		Notes
	< 14	≥ 14 through ≤ 28 ^a	
Visit Window (n days from parent study EOT)	< 14	≥ 14 through ≤ 28 ^a	
Eligibility and Disease Assessments			
Informed Consent	X	X	Appendix 2 (Study Governance)
Inclusion/Exclusion Criteria	X	X	Section 6 (Study Population)
Obtain Participant Number (IRT)	X	X	Section 7.2 (Method of Treatment Assignment)
Tobacco/e-Cigarette Use	X	X	Section 6.3.2 (Tobacco and e-Cigarettes)
Medical History ^b	X	X	Section 9.2.1
Concomitant Medication Use ^c	PSEOT ^k	X	Section 7.7 (Concomitant Therapy)
Physical Examination			
Physical Examination	PSEOT ^k	X	Section 9.4.2 (Physical Examinations)
Vital Signs (heart rate, blood pressure, temperature)	PSEOT ^k	X	Includes body temperature and seated blood pressure and heart rate. Blood pressure and heart rate should be measured after the participant has been resting quietly for at least 5 minutes.
Height	X	X	The height measurement should not be collected at Day 1. This height measurement should be carried over from the parent study screening visit and entered into Study IM011077 database (eg, eCRF).
Weight	PSEOT ^k	X	

[figure not shown]

Table 2-1: Day 1 Procedural Outline IM011077 From Parent Study IM011023 - Crohn's Disease

Procedure	Day 1		Notes
	< 14	≥ 14 through ≤ 28 ^a	
Visit Window (n days from parent study EOT)	< 14	≥ 14 through ≤ 28 ^a	
ECG	PSEOT ^k	X	Section 9.4.4 (Electrocardiograms)
Blood, Urine, and Fecal Tests			
Hematology and Chemistry	PSEOT ^k	X	Section 9.4.5 (Clinical Safety Labs)
Calculate eGFR	X	X	Exclusion Criterion 5(e)(ii)
Coagulation	PSEOT ^k	X	
Fasting Lipid Panel and Glucose	PSEOT ^k	X	Section 9.4.5 (Clinical Safety Labs)
Tuberculosis Risk Assessment	X	X	Appendix 5 (TB)
FSH	X	X	Appendix 4
Urine Pregnancy Test ^f	PSEOT ^k	X	Section 9.2.5 (Pregnancy); Section 9.4.5 (Clinical Safety Labs); Appendix 4
Urinalysis and Urine Chemistry	X	X	Section 9.4.5 (Clinical Safety Labs)
Pharmacokinetic Assessments	PSEOT ^k	X	See Table 9.5-1 for sample collection details.

Table 2-1: Day 1 Procedural Outline IM011077 From Parent Study IM011023 - Crohn's Disease

Procedure	Day 1		Notes
Visit Window (n days from parent study EOT)	< 14	≥ 14 through ≤ 28 ^a	
Endoscopy and Endoscopic Biopsies			
Endoscopy (ileocolonoscopy)	PSEOT		Section 9.1.1 (Endoscopies and Biopsies)
Additional Efficacy Assessments			
Health-Outcomes Assessments			

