^f Serum pregnancy test can be performed as an alternative to urine pregnancy test, based on the clinical judgment of the investigator. A serum pregnancy test should be performed prior to IP administration in WOCBP where a urine pregnancy test does not adequately exclude a clinical suspicion of pregnancy.

█ [REDACTED]

█ [REDACTED]

█ [REDACTED]

j On Day 1, after informed consent, study treatment should be taken from Study IM011077.

k Assessment will be performed during the PSEOT visit per protocol. Any missing data should be collected on Day 1.

Table 2-2: Year 1 Procedural Outline (IM011077) - Crohn's Disease

Procedure	Week 12 (Day 85)	Week 24 (Day 169)	Week 36 (Day 253)	Week 48 (Day 337) (or ET)	Final Safety Visit (28 days after ET)	Notes
Visit Window (\pm n days)	14	14	14	14	3	
Eligibility and Disease Assessments						
Tobacco/e-Cigarette Use	X	X	X	X	X	Section 6.3.2 (Tobacco and e-Cigarettes)
Concomitant Medication Use	X	X	X	X	X	Section 7.7 (Concomitant Therapy)
Physical Examination						
Physical Examination				X	X	Section 9.4.2 (Physical Examinations)
Targeted Physical Examination	X	X	X			Section 9.4.2 (Physical Examinations)
Vital Signs (heart rate, blood pressure, temperature)	X	X	X	X	X	Includes body temperature and seated blood pressure and heart rate. Blood pressure and heart rate should be measured after the participant has been resting quietly for at least 5 minutes.
Weight	X	X	X	X	X	
[REDACTED]						
ECG				X	X ^a	Section 9.4.4

Table 2-2: Year 1 Procedural Outline (IM011077) - Crohn’s Disease

Procedure	Week 12 (Day 85)	Week 24 (Day 169)	Week 36 (Day 253)	Week 48 (Day 337) (or ET)	Final Safety Visit (28 days after ET)	Notes
Blood, Urine, and Fecal Tests						
Hematology and Chemistry	X	X	X	X	X	Section 9.4.5 (Clinical Safety Labs)
Coagulation				X	X	
Fasting Lipid Panel and Glucose				X		Section 9.4.5 (Clinical Safety Labs)
Tuberculosis Risk Assessment				X		Appendix 5 (TB)
Urine Pregnancy Test ^d	X	X	X	X	X	Section 9.2.5 (Pregnancy); Section 9.4.5 (Clinical Safety Labs); Appendix 4
Urinalysis and Urine Chemistry	X			X	X	Section 9.4.5 (Clinical Safety Labs)
Pharmacokinetic Assessments	See Table 9.5-1 for sample collection details.					

Table 2-2: Year 1 Procedural Outline (IM011077) - Crohn’s Disease

Procedure	Week 12 (Day 85)	Week 24 (Day 169)	Week 36 (Day 253)	Week 48 (Day 337) (or ET)	Final Safety Visit (28 days after ET)	Notes
Endoscopy and Endoscopic Biopsies						

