Studies IM011023 and IM011024 include a double-blind placebo-control period of 52 weeks followed by a 52-week open-label extension (OLE) period. Study IM011127 includes a 12-week double-blind control period followed by a 40-week OLE period. Deucravacitinib is dosed at 6 mg BID in all parent study OLE periods.

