5.1.1 Qualification and Enrollment into Study

At the end of treatment visit for the parent IBD study (ie, Studies IM011023, IM011024, and IM011127), the end of treatment procedures will be performed per protocol. Participants who successfully complete the protocol-required treatment period with an acceptable safety profile, are in clinical response or clinical remission, *and* who have no worsening on endoscopy by Simple Endoscopic Score for CD (SES-CD) [REDACTED] or Mayo endoscopic subscore ([Appendix 13](#)) from the parent study baseline (as assessed by local read) may be eligible to participate in Study

IM011077. The end of treatment visit for the parent IBD study will also be the baseline visit (Day 1) of Study IM011077.

Prior to enrollment into Study IM011077, the investigator will evaluate whether the participants remain qualified for continued long-term participation based on the inclusion and exclusion criteria listed in [Section 6](#) (Study Population).

Participants entering Study IM011077 will not be expected to complete the [REDACTED] safety follow-up period of the parent study and are expected to transition into Study IM011077 from the end of treatment visit of the parent study. If same-day transition does not occur between the parent study end of treatment and Day 1 of Study IM011077, participants must enter the study within [REDACTED] (see below for exceptions) of the end of treatment visit of the parent study. The end of treatment assessments should be repeated as indicated in [Section 2](#) (Schedule of Activities). The only exception to this [REDACTED] is when the delay is due to clinical or regulatory issues (eg, resolution or treatment for an otherwise exclusionary AE, clinical laboratory value, or delayed Institutional Review Board [IRB]/Independent Ethics Committee [IEC] approval), investigators must discuss a participant's continued participation with the BMS Medical Monitor/designee prior to enrolling the participant.

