Relevant laboratory and endoscopy data, along with clinical and patient-reported outcome (PRO) assessments from the end of treatment visit in the parent study will constitute the baseline measures for Study IM011077 (see [Section 10.4.1.1](#) [Definition of Baseline] for a full description of how baseline will be derived for efficacy parameters). Depending on the timing of when a participant enters Study IM011077 (ie, visit window), these procedures may or may not be repeated at the Day 1 visit as indicated in [Section 2](#) (Schedule of Activities). The data from this visit will be entered into both the parent study and Study IM011077 databases (eg, eCRFs). Any assessments specific to Study IM011077 must be performed after the informed consent and prior to dispensation of study treatment.

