 - iii) Treatment with D-penicillamine, leflunomide, thalidomide, S1P inhibitors (eg, ozanimod, fingolimod, and etrasimod), or JAK inhibitors (eg, tofacitinib, upadacitinib, and filgotinib).
- b) Are currently receiving or require initiation of any of the following therapies:
 - i) Treatment with corticosteroids at a dose that exceeds the prednisone equivalent of [REDACTED] for adrenal insufficiency.
 - ii) Treatment with immunomodulatory agents (eg, azathioprine, 6-mercaptopurine, or methotrexate).
- c) Treatment with a live vaccine or live attenuated vaccine within [REDACTED] prior to Visit 1 of this trial.
Not applicable per Global Protocol Amendment 01.
Not applicable per Global Protocol Amendment 01.
Not applicable per Global Protocol Amendment 01.
- d) Not applicable per Global Protocol Amendment 01.
- e) Prophylactic antibiotic use should be discussed with the BMS Medical Monitor/designee.

5) Physical and Laboratory Test Findings

- a) Evidence of active or latent tuberculosis (TB; see [Section 9.4.6](#))
Participants diagnosed with latent TB infection (LTBI) in the parent study are eligible to continue in this study if (1) there are no current signs or symptoms of active TB, (2) the participant has received adequate documented treatment for LTBI within 5 years of screening in the parent study.
- b) Evidence of active hepatitis B virus (HBV) infection as defined in [REDACTED]
[REDACTED]
- c) Not applicable per Global Protocol Amendment 01.
- d) Not applicable per Global Protocol Amendment 01.
- e) Clinically significant abnormalities in laboratory testing at the second to last visit in the parent study or most current result available prior to Day 1 including (but not limited to):
 - i) **Hematology:**
 - (1) Hemoglobin level [REDACTED] g/dL
 - (2) White blood cell (WBC) count [REDACTED] $\times 10^9/L$ ($< 3000/mm^3$)
 - (3) Lymphocyte count [REDACTED] $\times 10^9/L$ ($< 750/mm^3$)
 - (4) Neutrophil count [REDACTED] $\times 10^9/L$ ($< 1000/mm^3$)
 - (5) Platelet count [REDACTED] $\times 10^9/L$ ($< 100,000/mm^3$)

ii) Renal Function:

- (1) Serum creatinine $> 2 \times$ upper limit of normal (ULN) or renal impairment based on an estimated glomerular filtration rate < 45 mL/min/1.73 m² (calculated using the Modification of Diet in Renal Disease equation)

iii) Liver-related Blood Tests and Liver Function:

- (1) Serum alanine aminotransferase (ALT) $> 2 \times$ ULN
- (2) Serum aspartate aminotransferase (AST) $> 2 \times$ ULN

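### For women of childbearing potential entering 2 to 13 days after the parent end-of-treatment visit, the pregnancy test carried over by the Day 1 schedules cannot meet the 24-hour limit in inclusion criterion 3(a)(iv)

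*Combined protocol and SAP*

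**What the plan says.** Section 6.1, criterion 3(a)(iv), requires a negative, highly sensitive urine pregnancy test in women of childbearing potential "within 24 hours prior to the start of study treatment". Section 6.2.1 requires the inclusion criteria to hold at the Day 1 enrollment visit and ties them to the first deucravacitinib dose in this study.

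The Day 1 schedules for the three parent studies (Tables 2-1, 2-4 and 2-5) have two columns: entry fewer than 14 days after the parent end-of-treatment (EOT) visit, and entry at 14 to 28 days. In all three, the row "Urine Pregnancy Test ^f" is marked PSEOT (parent study end of treatment) with footnote k in the first column, and X in the second. Footnote k reads: "Assessment will be performed during the PSEOT visit per protocol. Any missing data should be collected on Day 1".

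Section 5.1.1 says that participants "are expected to transition into Study IM011077 from the end of treatment visit of the parent study", allows later entry, and leaves repetition to the schedules: "these procedures may or may not be repeated at the Day 1 visit as indicated in" Section 2.

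**The concern.** The schedule and the criterion set different rules for the same test. The criterion limits the test's age to 24 hours. The schedule accepts a parent-visit test for any entry up to day 13, and Section 5.1.1 sends the site back to the schedule to learn what to repeat.

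Where the protocol means an older result to count, it says so. Laboratory exclusion 5(e) accepts results "at the second to last visit in the parent study or most current result available prior to Day 1". Criterion 3(a)(iv) has no such allowance.

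A site that follows the procedure row exactly, for a woman entering on days 2 to 13, has no qualifying test at first dose. If the eligibility check overlooks the test date, the result is an eligibility deviation and a missed pre-dose pregnancy test, in a protocol whose Section 9 permits no waivers.

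**Working it through.** No sample size, power or error rate is involved. The check compares the age of the carried-over test at first dose with the limit.

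**Inputs**
- Limit: 24 hours (Section 6.1, criterion 3(a)(iv)).
- Test date: the parent EOT visit, called day 0, for entry under 14 days (Tables 2-1, 2-4, 2-5, footnote k).
- First dose: Day 1 of IM011077, from IM011077 supply (footnote j), falling *d* calendar days after the parent visit.

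**Formulas**
- Nominal test age: *d* × 24 h.
- Shortest possible age for *d* ≥ 1 (test at the end of day 0, dose at the start of day *d*): just over (*d* − 1) × 24 h.
- Longest possible age: under (*d* + 1) × 24 h.

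**Results**

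| Entry day *d* | Shortest age | Nominal age | Longest age | Scheduled test | 24 h limit |
|---|---|---|---|---|---|
| 0 | 0 h | 0 h | < 24 h | carried over | met |
| 1 | > 0 h | 24 h | < 48 h | carried over | depends on clock time |
| 2 | > 24 h | 48 h | < 72 h | carried over | cannot be met |
| 13 | > 288 h | 312 h | < 336 h | carried over | cannot be met |
| 14 to 28 | – | – | – | repeated on Day 1 | can be met |

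The shortest age rises by 24 h per day, so every day from 2 to 13 fails. The under-14-day column holds days 0 to 13, which is 14 days. Days 2 to 13 are 12 of them: 12/14 = 85.7%. On those days the nominal age is 48/24 = 2 to 312/24 = 13 times the limit.

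**Could other text restore the limit?**
- *Footnote k.* A completed parent test is not missing data, so an out-of-date result does not trigger a Day 1 test.
- *Footnote f.* It allows a serum test as an alternative and requires one where the urine test leaves a clinical suspicion of pregnancy. It sets no time limit.
- *Start of study treatment read as the parent study's first dose.* Section 6.2.1 and footnote j both point to the IM011077 dose.
- *Criterion 3(a)(v).* It refers to Section 2 only for further testing during and after treatment, so it neither relaxes (iv) nor supplies the missing pre-dose test.

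**The case against.** The strongest reply is that the two texts can be obeyed together. The criterion is explicit, numbered and mandatory. The Day 1 tables mark the inclusion/exclusion check in both columns, and Sections 6.2.1 and 9 require eligibility to be confirmed before the first dose. Nothing forbids an extra test, so harm requires a site to overlook a clear criterion. Because (v) cites Section 2 only for later testing, the schedule can hardly be the authority for the pre-dose test. All of this stands. It makes the problem recoverable, but the row still omits a test that the criterion demands.

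A second reply is that Section 5.1.1 requires assessments specific to IM011077 to be done after consent and before dispensing, and that a test timed to the first IM011077 dose is one of these. That is arguable at best, because the urine test is also a parent EOT procedure and the same section sends repeat decisions to Section 2.

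Third, the safety consequence is small. This largely stands:
- "Deucravacitinib is dosed at 6 mg BID in all parent study OLE periods", so entrants come from treatment at the same dose.
- Contraception is an entry condition: "Is a WOCBP and using a contraceptive method(s) as described in" Appendix 4.
- Criterion 3(a)(vi) asks for a review of menstrual history and recent sexual activity.
- Section 3.3 reports no teratogenic or fetotoxic findings.
- Tables 2-2 and 2-6 schedule on-treatment tests every 12 weeks (12 × 7 = 84 days), against which a gap of up to 13 days is short.

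Finally, 12 of 14 weights calendar days equally although same-day entry is expected. That is correct: the fraction describes the column, not how often the problem will arise.

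**Conclusion.** The concern holds. For entry on days 2 to 13, all three Day 1 schedules rely on a pregnancy test that is necessarily older than criterion 3(a)(iv) allows. Day 1 is borderline, and day 0 and days 14 to 28 are unaffected. This rests on reading the start of study treatment as the first IM011077 dose and on counting entry in calendar days from the parent EOT visit. It does not depend on any redacted text.

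The number of women of childbearing potential with delayed entry is not given, so the number of participants affected cannot be estimated. The consequence is a risk of eligibility deviations and missed pre-dose tests, with modest safety impact. No endpoint, analysis or estimate changes. It should be corrected because the row contradicts a mandatory criterion and compliance depends on staff noticing the omission.

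**What to change.** In the urine pregnancy test row of Tables 2-1, 2-4 and 2-5, change the under-14-day cell to: *PSEOT only if within 24 hours before first IM011077 dose; otherwise repeat on Day 1 before dosing*. Remove footnote k from that row. Leave criterion 3(a)(iv) as it is. Every entry day in the column can then meet the limit.

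The cost is one cell in three tables, by amendment or administrative letter, and at most one urine test per woman, which the criterion already demands, at a visit that already takes place.
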